2.8.2 Deaths

The number and percentage of deaths resulting from TEAEs will be summarized by SOC and PT. All the deaths in the clinical database including those occurring during screening will be listed.

Secondary endpoint: the rate of patient deaths due to a treatment emergent asthma exacerbation

The number and percentage of deaths due to a treatment emergent asthma exacerbation will be summarized.

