If discontinuation of study treatment occurs, the patient should NOT be considered withdrawn from the study. The patient should return to the clinic as soon as possible, after discontinuation of study drug, for a study treatment discontinuation visit. Treatment discontinuation visit assessments detailed in the “unscheduled treatment discontinuation visit” (TD) in [Table 6-1](#) should be completed and recorded in the eCRF. The investigator must determine the primary reason for the patient’s premature discontinuation of study treatment and record this information on the Dosage Administration eCRF.

Patients who discontinue study treatment will be asked to remain in the study and complete all study visits. Patients withdrawn from study treatment will receive SoC asthma therapy according to investigator judgment.

If the patient cannot or is unwilling to attend any visit(s), the site staff should maintain regular telephone contact with the patient, or with a person pre-designated by the patient. This telephone contact should preferably be done according to the study visit schedule. Data will continue to be collected concerning the patients' condition and changes in concomitant medications, surgeries and procedures, serious and non-serious adverse events, and asthma exacerbations should be recorded in the appropriate eCRF if applicable. If necessary an unscheduled clinical visit may be arranged.

The investigator must also contact the IRT to register the patient's discontinuation from study treatment.

If study drug discontinuation occurs because treatment code has been broken, please refer to [Section 5.5.10](#)

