- overall by system organ class, preferred term and maximum severity,
- suspected drug-related AEs by system organ class and preferred term,
- SAEs by system organ class and preferred term, and
- AEs leading to permanent discontinuation of study-drug by system organ class and preferred term.

Additionally, summaries including both treatment emergent and post-treatment discontinuation events will be produced for AEs and SAEs by system organ class and preferred term. Similarly, summaries will also be presented on patient deaths and patient hospitalizations (any visit to the hospital requiring an overnight stay or an emergency room visit greater than 24 hours) due to an asthma exacerbation.

The number and percentage of patients with treatment emergent AEs of special interest (e.g., IDRs), will be summarized for each type of event with a break-down for each type of event by SMQ (when applicable) and preferred term. Time-to-first-event analyses using Kaplan-Meier plots and Cox regressions with the same model terms as the primary efficacy analysis model will be reported for each type of event, as well as incidence for recurrent events per patient-year of follow-up. The strategy for identifying these events will be defined in the detailed statistical analysis plan for this study.

Vital signs

On-treatment data from the vital signs (body temperature, systolic blood pressure, diastolic blood pressure, and pulse rate) will be summarized by treatment and scheduled visit. The maximum and minimum on-treatment systolic blood pressure, diastolic blood pressure, and pulse rate post-baseline (including values from post-baseline unscheduled and premature discontinuation visits) will also be summarized by treatment. Absolute on-treatment body weight will be summarized by scheduled visit. The on-treatment change from baseline to each scheduled post-baseline visit will be summarized by vital sign parameter, scheduled visit and treatment with standard descriptive statistics.

Notable on-treatment values and notable on-treatment changes from baseline in vital signs will be summarized.

Electrocardiogram (ECG)

The on-treatment changes from baseline will be summarized by ECG parameter, scheduled visit where baseline and post baseline values are both available.

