2.5 Analysis of the primary objective

2.5.1 Primary endpoint

Primary endpoints for the study are:

Treatment Period 1:

- Time-to-first treatment emergent adverse events (AEs);
- Time-to-first treatment emergent serious adverse events (SAEs); and
- Time-to-first treatment emergent AE leading to discontinuation from study treatment.

of QAW039 (150 mg once daily and 450 mg once daily), compared with placebo in patients with moderate-to-severe asthma receiving SoC asthma therapy.

Treatment Period 1 and Treatment Period 2 combined:

- Time-to-first treatment emergent adverse events (AEs);
- Time-to-first treatment emergent serious adverse events (SAEs); and
- Time-to-first treatment emergent AE leading to discontinuation from study treatment.

of QAW039 (150 mg once daily and 450 mg once daily), compared with placebo in patients with moderate-to-severe asthma receiving SoC asthma therapy.

As this study has been early terminated, the primary endpoint will be analyzed in the way of combined treatment period 1 and treatment period 2. Treatment emergent AEs are defined as adverse events (including asthma exacerbations), starting on or after the day of the first intake of study drug in this study and until the earlier date out of: date of last intake of study drug +7 days (30 days in the case of a serious AE) and final visit.

Any AEs that started during the study after informed consent and before the time of the first intake of study drug will be classified as a prior AE and not classified as treatment emergent AE. The time-to-first treatment emergent AE is defined as the time to the occurrence of an AE from the treatment start date, and computed as time to AE=AE start date – treatment start date +1 day. As a general rule of censoring, patients who either completed the study or discontinued

treatment prematurely or continued treatment and without the event of interest will be censored at the minimum out of the dates of last medication intake + 30 days, final visit date, and date of death. Time-to-first treatment emergent SAEs and time-to-first treatment emergent AEs leading to discontinuation from study treatment are defined in a similar manner as time-to-first treatment emergent AE.

The definition and rationale for the estimand for the primary endpoint are given in [Table 2-1](#). The statistical strategy to handle each intercurrent event is described in more detail in [Section 2.5.3](#).

Table 2-1 Summary of estimand for the primary endpoint

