In safety analysis, each record of asthma exacerbation episode will be considered as an adverse event regardless of the interval between two episodes, i.e., no collapsing of multiple records (this differs from how asthma exacerbations are included in efficacy analyses – see Section 2.13.1). Number of treatment emergent severe asthma exacerbation episodes requiring hospitalizations (any visit to the hospital requiring an overnight stay or an emergency room visit greater than 24 hours) will be summarized by source of patients.

Adverse events of special interest / grouping of AEs

AEs of special interest definitions are found in the compound electronic Case Retrieval Strategy (eCRS). The classification reflects the current version of the dSPP and might be updated based on review of accumulating data. To identify AEs of special interest at the time of the final analysis, the latest version of the eCRS where Core safety topic risk (SP) = 'Yes' or Other Search risk (OS) = 'Yes' will be used.

The number and percentage of patients with treatment emergent AEs of special interest will be summarized by risk category, PT, treatment on overall population and by source of patients. In addition, summaries will be provided for

- Treatment emergent AEs of special interest by maximum severity
- Treatment emergent serious AEs of special interest
- Treatment emergent AEs of special interest that are suspected to be related to study drug

AE reporting for CT.gov and EudraCT

For the legal requirements of clinicaltrials.gov and EudraCT, two required tables on treatment emergent adverse events which are not serious adverse events with an incidence greater than X% and on treatment emergent serious adverse events and SAE suspected to be related to study treatment will be provided by system organ class and preferred term on the safety set population.

If for a same patient, several consecutive AEs (irrespective of study treatment causality, seriousness and severity) occurred with the same SOC and PT:

- a single occurrence will be counted if there is ≤ 1 day gap between the end date of the preceding AE and the start date of the consecutive AE
- more than one occurrence will be counted if there is > 1 day gap between the end date of the preceding AE and the start date of the consecutive AE

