For occurrence, the presence of at least one SAE / SAE suspected to be related to study treatment / non SAE has to be checked in a block e.g., among AE's in a ≤ 1 day gap block, if at least one SAE is occurring, then one occurrence is calculated for that SAE.

The number of deaths resulting from SAEs suspected to be related to study treatment and SAEs irrespective of study treatment relationship will be provided by SOC and PT.

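### SAP 2.8.2 limits both of its death tables to treatment-emergent events, and no other planned table clearly shows later deaths by treatment group

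*SAP*

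**What the plan says.** SAP 2.8.2 provides two tables and one listing:

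- All causes: "The number and percentage of deaths resulting from TEAEs will be summarized by SOC and PT".
- Asthma deaths, as a secondary endpoint: "The number and percentage of deaths due to a treatment emergent asthma exacerbation will be summarized".
- Listing: "All the deaths in the clinical database including those occurring during screening will be listed".

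SAP 2.5.1 ends the treatment-emergent window at the earlier of "date of last intake of study drug +7 days (30 days in the case of a serious AE) and final visit".

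SAP 2.8.1 has two further provisions that bear on late deaths. Under registry reporting: "The number of deaths resulting from SAEs suspected to be related to study treatment and SAEs irrespective of study treatment relationship will be provided", by system organ class and preferred term. Separately, events starting after the treatment-emergent window are summarised as a count and percentage of patients having any such event.

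Protocol 5.6.2 says: "Patients who discontinue study treatment will be asked to remain in the study and complete all study visits". Table 6-1 schedules the recording of deaths throughout the visit schedule, and Protocol 5.6.1 collects survival status at Visit 401.

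Protocol 9.5.2 says that "summaries including both treatment emergent and post-treatment discontinuation events will be produced for AEs and SAEs by system organ class and preferred term", and that deaths and hospitalisations due to an asthma exacerbation will be summarised in the same way. It also plans a supportive rate analysis of those asthma outcomes that counts events both on treatment and after stopping.

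**The concern.** In a long-term safety trial, death is the outcome least open to reporting bias. It is also the one for which a comparison over all follow-up, as randomised, is most useful. If the tables count only deaths from events that start on drug or shortly after, the comparison depends on who stops treatment and when. A patient who stops because of decline, and dies of an event that begins two months later, is outside both 2.8.2 tables. If stopping differs between arms, the excluded follow-up differs too.

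The protocol had planned for this at least for asthma deaths, and the SAP does not visibly carry that plan forward.

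**Working it through.** **Step 1: trace one death.** Take a patient who stops drug, stays in the study, and dies of a serious event that starts 60 days after the last dose.

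| Planned output | Is the death shown as a death? |
|---|---|
| SAP 2.8.2, deaths from treatment-emergent events | No: onset is after day 30 |
| SAP 2.8.2, deaths from treatment-emergent asthma exacerbation | No, for the same reason |
| SAP 2.8.1, registry death count | Unclear (step 2) |
| SAP 2.8.1, post-treatment events | Counted as a patient with an event, with no breakdown by fatal outcome |
| SAP 2.8.2, listing | Yes |

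**Step 2: scope of the registry count.** The sentence does not itself limit deaths to treatment-emergent events. It closes a sub-section whose SAE table is described as covering "treatment emergent serious adverse events and SAE suspected to be related to study treatment will be provided by system organ class". Its phrase about relationship concerns causality, not timing. Either reading is possible. Neither this sentence nor SAP 2.8.2 states that results are given by treatment group, and the count has no split by time and no follow-up denominator.

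**Step 3: protocol against SAP.** Protocol 9.5.2 plans the asthma-death summaries and the supportive analysis with post-discontinuation events included. The visible SAP has only the treatment-emergent asthma-death table. The visible entries in SAP section 4 say that post-treatment events are summarised separately, that the supportive analyses of Protocol 9.4.4 (a different section) move to incidence-rate summaries, and that the treatment-emergent window was changed. None says that the asthma-death summaries of 9.5.2 are dropped. Parts of that list are redacted.

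**Step 4: size.** The documents give no figure to reproduce. Inputs: censoring rates 0.22 (placebo) and 0.16 (QAW039) and N = 1,570 from SAP section 3; allocation of about 3:3:1 from Protocol 3.1. Assumptions: the rates are per patient-year and mean stopping treatment, and everyone is followed to the planned end.

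With w = 30/365.25 = 0.082 years and h = T − w:

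- Share stopping more than 30 days before T: 1 − exp(−r·h)
- Mean years per patient beyond last dose + 30 days: h − (1 − exp(−r·h))/r

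| T | Arm | Share stopping | Years per patient | Share of follow-up |
|---|---|---|---|---|
| 1 year | Placebo | 18.3% | 0.087 | 8.7% |
| 1 year | QAW039 | 13.7% | 0.064 | 6.4% |
| 3 years | Placebo | 47.4% | 0.765 | 25.5% |
| 3 years | QAW039 | 37.3% | 0.586 | 19.5% |

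Arm sizes are 1,570/7 ≈ 224 on placebo and 3 × 1,570/7 ≈ 673 on each dose. Total patient-years beyond last dose + 30 days:

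- 1 year: 224 × 0.087 + 2 × 673 × 0.064 ≈ 106
- 3 years: 224 × 0.765 + 2 × 673 × 0.586 ≈ 960

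The documents give no mortality rate. Assuming 1 to 5 deaths per 1,000 patient-years, this is about 0.1 to 0.5 deaths at 1 year and 1 to 5 at 3 years, over all arms.

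**The case against.** The strongest case against is that little is lost. Every death is listed, so late deaths can be found by hand. The trial ended early, Treatment Period 2 was optional, and some censored patients will have left the study, so the follow-up shares above are upper bounds. The SAP counts by onset of the event, so a death on day 60 from an event that began on day 20 is already in the table. The expected number of late deaths is small. All of this stands, and it keeps the point modest.

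Four stronger readings might be inferred, and the documents do not support them.

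- *Late deaths are in no table at all.* The registry count in SAP 2.8.1 may include them; its scope is ambiguous, not shown to be narrow.
- *The SAP dropped a promised all-cause death comparison.* The visible protocol promises post-discontinuation summaries of deaths only where they are due to asthma. An all-cause table would be an addition.
- *The SAP narrowed the asthma-death endpoint.* The protocol's endpoint was itself treatment emergent, with a window ending the day after last intake. The SAP extends it to 30 days for serious events and declares the change.
- *The follow-up shares are shares of deaths.* They would be so only under constant mortality and counting by date of death. The plan also calls the rates censoring rates, so reading them as differential stopping of treatment is an assumption.

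The objection does not remove two things. A listing gives no comparison between arms, and the ambiguity of the registry count is itself a reason to clarify the text.

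**Conclusion.** The point holds in a limited form. Both tables in SAP 2.8.2 stop at treatment-emergent events, and the listing is the only output certain to show a death from an event that starts more than 30 days after last dose. The protocol's asthma-death summaries covering events after discontinuation are missing from the visible SAP, with no visible declaration. Because of redaction, an undisclosed entry cannot be excluded.

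The size is uncertain and probably small in deaths. Under the stated assumptions the uncovered follow-up per patient is about 1.3 to 1.4 times larger on placebo than on QAW039 (0.765/0.586 and 0.087/0.064). Early termination moves the trial toward the 1-year figures. The reason to act is that the change is nearly free and gives a long-term safety trial a death comparison that does not depend on when patients stop drug.

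**What to change.** In SAP 2.8.2:

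1. Add one table of all deaths from first dose in A2315 to last contact, by treatment group, split into treatment emergent and post-treatment, with patient-years of follow-up.
2. Give the same table for deaths due to asthma exacerbation, which restores the summary planned in Protocol 9.5.2. Otherwise, declare its removal in SAP section 4.
3. Keep the existing table based on treatment-emergent events.

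In SAP 2.8.1, state whether the registry death count is limited to treatment-emergent SAEs.

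The cost is a small amount of programming on deaths already in the database and already listed. The downside is that late off-drug deaths unrelated to treatment enter the total; the split makes them visible.

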2.8.3 Laboratory data

Laboratory data consist of hematology, biochemistry and urinalysis. On-treatment laboratory data will be summarized. Laboratory data measured on or after first intake of study drug and until 7 days after last intake of study drug are regarded as on-treatment data. All data will be included in the analyses regardless of rescue medication use. The following sub-sections will describe the method of summary. For rollover patients, the last pre-treatment assessment in the current study (A2315 baseline) will be used in summary tables and figures. Prior study baseline will be considered as a supplementary baseline value presented in figures as well.

2.8.3.1 Summary of absolute values

For all continuous laboratory parameters, the absolute laboratory values, including the worst case post-baseline values (including values from post-baseline unscheduled and premature discontinuation visits), will be summarized with standard descriptive statistics by parameter, scheduled visit and treatment. The direction of interest for worst case post-baseline for selected hematology and biochemistry parameters is tabulated in [Table 2-2](#).

For categorical urinalysis laboratory parameters, a frequency table of results will be produced by laboratory parameter, scheduled visit, and treatment for the whole study duration.

2.8.3.2 Summary of change from baseline

For continuous laboratory parameters, the change from baseline at each scheduled visit, and the change from baseline to the worst case post-baseline values (including values from post-baseline unscheduled and premature discontinuation visits) will be summarized by laboratory parameter, scheduled visit, and treatment with standard descriptive statistics.

2.8.3.3 Notable values

For selected laboratory parameters, abnormalities occurring at any time-point over the treatment period, considering all post-baseline on-treatment data from scheduled, unscheduled and premature discontinuation visits will be summarized.

Patients with any newly occurring or worsening on-treatment value meeting the clinically notable criteria will be counted under the applicable criteria. For a patient to meet the criterion of a newly occurring clinically notable value, the patient needs to have a baseline value which is not clinically notable for that parameter. For a patient to meet the criterion of a worsening clinically notable value, the patient needs to have a baseline value which is clinically notable and also have a worse post-baseline value. For patients with missing value in baseline, any post-baseline notable value will be considered as newly occurring.

Guidelines for clinically notable criteria for laboratory tests are based on the FDA Guidelines for adults in SI units. The criteria for clinically notable values are presented in [Table 2-3](#).

Laboratory test units will be converted to standard units. Based on agreement within our standards, if we have a multi-region study the Blood Urea Nitrogen (BUN) / Urea test would be represented as BUN [mg/dL] for the regions used to conventional results (US, Latin America) and as Urea [mmol/L] for the regions used to SI results. Therefore both BUN and Urea parameters will be included in the listings.

BUN is always reported as mg/dL and Urea as mmol/L. BUN and Urea are the same measurement in the lab and should be considered the same test. Hence for the summary tables, it is expressed in SI units. Conversion to SI units includes the factor which incorporates a conversion from BUN to Urea as well as a conversion from mg/dL to mmol/L. This is necessary because BUN is Urea Nitrogen, not Urea and there are two nitrogens in each urea molecule. The factor of 0.357 converts BUN in mg/dL to Urea in mmol/L.

Listings of patients with notable laboratory values will be provided by laboratory parameter, treatment group, and patient number.

For summary tables and figures on laboratory parameters considering values, which are lower or greater than the limit of quantification, the following approach will be taken. For values which are flagged as lower than the lower limit of quantification, the values presented in summary tables should be multiplied by 0.5 and for values which are flagged as greater than upper limit of quantification as 1.5, the values presented in summary tables should be multiplied by 1.5. If either albumin or protein or creatinine is below the limit of quantification then the raw values would be imputed and ratios will be computed.

Additionally, box plot over time for Albumin: Creatinine ratio (ACR), Protein: Creatinine ratio (PCR) will be presented. Box plot of creatinine change from baseline values for the post-baseline visits will also be presented. Albumin: Creatinine ratio (ACR) value will be considered

missing if either the albumin or the creatinine values are missing. Similarly, Protein: Creatinine ratio (PCR) will be considered missing if either the protein or the creatinine values are missing. Mean change from baseline in creatinine will be plotted for the post-baseline visits.

Table 2-2 Direction of interest for worst case value for laboratory parameters

Laboratory parameter	Direction of interest for worst case value
A. Hematology	
Basophils	High
Eosinophils	High
Hematocrit	Low
Hemoglobin	Low
Lymphocytes	Low and high
Monocytes	High
Neutrophils	Low and high
Platelets	Low and high
RBC	Low
WBC total	Low and high
B. Chemistry	
Albumin	Low
Sodium	Low and High
Alkaline Phosphatase	High
ALT/SGPT	High
AST/SGOT	High
Bilirubin Total	High
Blood Urea Nitrogen (BUN)	High
CPK	High
Creatinine	High
Gamma GT	High
Glucose	Low and high
Potassium	Low and high
Uric acid	High

Table 2-3 Clinical notable criteria for selected laboratory tests

Laboratory parameter (unit)	Bound for notably low values	Bound for notably high values
Hematology		
Hematocrit (v/v)		
Male 12-17	0.34	
Male 18-65	0.37	
Male >=66	0.34	
Female 12-65	0.32	
Female >=66	0.31	
Hemoglobin (g/L)		
Male 12-17	100	

Laboratory parameter (unit)	Bound for notably low values	Bound for notably high values
Male >=18	110	
Female	95	
Thrombocytes (x10E ⁹ /L)	75	700
WBC's (x10 ⁹ /L)	2.8	16.0
Chemistry		
Alkaline Phosphatase (IU/L)	-	3xULN
Total Bilirubin (µmol/L)	-	34.2
Creatinine (µmol/L)		176.8
Potassium (mmol/L)	3	6
Glucose (mmol/L)	2.78	9.99
ALT/SGPT (U/L)	-	3 x ULN
AST/SGOT (U/L)	-	3 x ULN
BUN/ Urea (mmol/L)		9.99
Sodium (mmol/L)	125	160
Gamma GT (U/L)		3 x ULN
CPK (IU/L)		4 x ULN
Urinalysis		
Dipstick blood		≥ 2+
Dipstick glucose		≥ 2+
Dipstick leukocytes		≥ 2+
Dipstick protein		≥ 2+
v = volume, ULN = upper limit of normal		

Liver function tests

To evaluate potential drug-induced liver injury, newly occurring or worsening abnormalities in liver function tests will be evaluated (see Table 2-4 for a summary of the notable values).

When a criterion contains multiple laboratory parameters, the criterion will only be considered to be met when all conditions occur at the same time (i.e., in the same sample). A case where all criteria are met at a post-baseline time point but not met at baseline will be considered as newly occurring. A case will be considered as worsening if all the criteria are met at baseline and at least one component is worsening from baseline, irrespective of whether the other(s) are better.

The number and percentage of patients with newly occurring liver enzyme abnormalities any time post-baseline will be summarized by source of patients. Listings of patients with notable liver function test lab values and liver events will be provided.

To evaluate drug induced serious hepatotoxicity eDish plots will be presented by source of patients and treatment in prior study for rollover for rollover patients. The eDish plot will reflect the worst value of each of the parameters; they do not need to occur at the same visit.

Table 2-4 Notable liver function test values

Criterion
ALT > 3 x ULN ALT > 5 x ULN ALT > 8 x ULN ALT > 10 x ULN ALT > 20 x ULN
ALT or AST > 3 x ULN ALT or AST > 5 x ULN ALT or AST > 8 x ULN ALT or AST > 10 x ULN ALT or AST > 20 x ULN
Total Bilirubin > 1 x ULN Total Bilirubin > 1.5 x ULN Total Bilirubin > 2 x ULN Total Bilirubin > 3 x ULN
ALP > 1.5 x ULN ALP > 2 x ULN ALP > 3 x ULN ALP > 5 x ULN
ALT or AST > 3 x ULN and Total Bilirubin > 1.5 x ULN ALT or AST > 3 x ULN and Total Bilirubin > 2 x ULN ALT or AST > 5 x ULN and Total Bilirubin > 2 x ULN ALT or AST > 8 x ULN and Total Bilirubin > 2 x ULN ALT or AST > 10 x ULN and Total Bilirubin > 2 x ULN ALT or AST > 20 x ULN and Total Bilirubin > 2 x ULN
ALP > 3 x ULN and Total Bilirubin > 2 x ULN ALP > 5 x ULN and Total Bilirubin > 2 x ULN
ALT or AST > 3 x ULN and Total Bilirubin > 2 x ULN and ALP ≤ 2 x ULN (Hy's law)
ALT or AST > 3 x ULN and (nausea or vomiting or fatigue or general malaise or abdominal pain or (rash and eosinophilia))*

ALT=alanine aminotransferase; AST=aspartate aminotransferase; ALP=alkaline phosphatase; ULN=upper limit of normal. *Based on the signs/symptoms information as recorded on the liver events eCRF, not the adverse events eCRF.

